Appendix 3. Study Governance, Regulatory and Ethical Considerations

Informed Consent

The investigator is responsible for:

- ensuring that the subject understands the potential risks and benefits of participating in the study.
- ensuring that informed consent is given by each subject or legal representative. This includes obtaining the appropriate signatures and dates on the ICF prior to the performance of any protocol procedures and prior to the administration of IP.
- answering any questions the subject may have throughout the study and sharing in a timely manner any new information that may be relevant to the subject's willingness to continue his or her participation in the trial.

Ethical Review

The investigator or appropriate local representative must give assurance that the ERB was properly constituted and convened as required by (ICH) guidelines and other applicable laws and regulations.

Documentation of ERB approval of the protocol and the ICF must be provided to Lilly before the study may begin at the investigative site(s). Lilly or its representatives must approve the ICF before it is used at the investigative site(s). All ICFs must be compliant with the ICH guideline on GCP.

The study site's ERB(s) should be provided with the following:

- the current IB and updates during the course of the study;
- ICF;
- relevant curricula vitae.

Regulatory Considerations

This study will be conducted in accordance with:

- 1) consensus ethics principles derived from international ethics guidelines, including the Declaration of Helsinki and Council for International Organizations of Medical Sciences (CIOMS) International Ethical Guidelines;
- 2) applicable ICH GCP Guidelines;
- 3) applicable laws and regulations.

Some of the obligations of the sponsor will be assigned to a third party organization.

Protocol Signatures

The sponsor's responsible medical officer will approve the protocol, confirming that, to the best of his or her knowledge, the protocol accurately describes the planned design and conduct of the study.

After reading the protocol, each principal investigator will sign the protocol signature page and send a copy of the signed page to a Lilly representative.

Final Report Signature

The investigator or designee will sign the clinical study report for this study, indicating agreement with the analyses, results, and conclusions of the report.

The sponsor's responsible medical officer and statistician will sign/approve the final clinical study report for this study, confirming that, to the best of his or her knowledge, the report accurately describes the conduct and results of the study.

Data Quality Assurance

To ensure accurate, complete, and reliable data, Lilly or its representatives will do the following:

- provide instructional material to the study sites, as appropriate;
- provide training to instruct the investigators and study coordinators. This training will give instruction on the protocol, the completion of the CRFs, and study procedures;
- make periodic visits to the study site;
- be available for consultation and stay in contact with the study site personnel by mail, telephone, and/or fax;
- review and evaluate CRF data and/or use standard computer edits to detect errors in data collection;
- conduct a quality review of the database.

In addition, Lilly or its representatives will periodically check a sample of the subject data recorded against source documents at the study site. The study may be audited by Lilly and/or regulatory agencies at any time. Investigators will be given notice before an audit occurs.

The investigator will keep records of all original source data. This might include laboratory tests, medical records, and clinical notes. If requested, the investigator will provide the sponsor, applicable regulatory agencies, and applicable ERBs with direct access to the original source documents.

Data Collection Tools/Source Data

An electronic data capture system will be used in this study. The site must define and retain all source records and must maintain a record of any data where source data are directly entered into the data capture system.

Study and Site Closure***Discontinuation of Study Sites***

Study site participation may be discontinued if Lilly or its designee, the investigator, or the ERB of the study site judges it necessary for medical, safety, regulatory, or other reasons consistent with applicable laws, regulations, and GCP.

Discontinuation of the Study

The study will be discontinued if Lilly or its designee judges it necessary for medical, safety, regulatory, or other reasons consistent with applicable laws, regulations, and GCP.

Appendix 4. Blood Sampling Summary

This table summarizes the approximate number of venipunctures and blood volumes for all blood sampling (screening, safety laboratories, and bioanalytical assays) during the study. Fewer venipunctures and blood draws may actually occur, but this will not require a protocol amendment.

Protocol I8K-MC-JPDF Sampling Summary

Purpose	Maximum Blood Volume per Sample (mL)	Maximum Number of Blood Samples	Maximum Total Volume (mL)
Screening tests ^a	17	1	17
Clinical laboratory tests ^a	11	13	143
Pharmacokinetics ^b	2	76	152
Pharmacogenetics	10	1	10
Total			322
Total for clinical purposes [rounded up to nearest 10 mL]			330

^a Additional samples may be drawn if needed for safety purposes.

^b Includes up to 2 additional samples per treatment period.

Leo Document ID = 703e9077-f89a-47f5-82ab-b423ca236f45

Approver: PPD
Approval Date & Time: 09-Jan-2017 13:48:54 GMT
Signature meaning: Approved

Approver: PPD
Approval Date & Time: 09-Jan-2017 13:53:47 GMT
Signature meaning: Approved

2. ABBREVIATIONS

Abbreviations pertain to the Statistical Analysis Plan (SAP) only (not the tables, figures and listings [TFLs]).

AE	Adverse event
API	Active pharmaceutical ingredient
AUC	Area under the concentration versus time curve
AUC(0-t _{last})	Area under the concentration versus time curve from time zero to time t, where t is the last time point with a measurable concentration
AUC(0-∞)	Area under the concentration versus time curve from zero to infinity
%AUC(t _{last} -∞)	Percentage of AUC(0-∞) extrapolated
BQL	Below the lower limit of quantitation
C _{last}	Last quantifiable drug concentration
C _{max}	Maximum observed drug concentration
CI	Confidence interval
CL/F	Apparent total body clearance of drug calculated after extra-vascular administration
CRF	Case Report Form
CRU	Clinical Research Unit
CSR	Clinical Study Report
CV	Coefficient of variation
EC	Early Clinical
ECG	Electrocardiogram
e.g.	For example (Latin: exempli gratia)
ICH	International Conference on Harmonisation
LLOQ	Lower limit of quantification
MedDRA	Medical Dictionary for Regulatory Activities
PK	Pharmacokinetic
PSD	Particle size distribution
SAP	Statistical Analysis Plan
SD	Standard deviation
TFLs	Tables, Figures, and Listings

$t_{1/2}$	Half-life associated with the terminal rate constant (λ_z) in non-compartmental analysis
t_{max}	Time of maximum observed drug concentration
V_{ss}/F	Apparent volume of distribution at steady state after extra-vascular administration
V_z/F	Apparent volume of distribution during the terminal phase after extra-vascular administration
WHO	World Health Organization

3. INTRODUCTION

This SAP has been developed after review of the Clinical Study Protocol (final version dated 09 January 2017).

This SAP describes the planned analysis of the safety, tolerability and pharmacokinetic (PK) data from this study. A detailed description of the planned TFLs to be presented in the clinical study report (CSR) is provided in the accompanying TFL shell document.

The intent of this document is to provide guidance for the statistical and PK analyses of data. In general, the analyses are based on information from the protocol, unless they have been modified by agreement between Eli Lilly and Company and CCI. A limited amount of information concerning this study (e.g., objectives, study design) is given to help the reader's interpretation. This SAP must be signed off prior to first subject administration for this study. When the SAP and TFL shells are agreed upon and finalized, they will serve as the template for this study's CSR.

This SAP supersedes the statistical considerations identified in the protocol; where considerations are substantially different, they will be so identified. If additional analyses are required to supplement the planned analyses described in this SAP, they may be performed and will be identified in the CSR. Any substantial deviations from this SAP will be agreed upon between Eli Lilly and Company and CCI and identified in the CSR. Any minor deviations from the TFLs may not be documented in the CSR.

This SAP is written with consideration of the recommendations outlined in the International Conference on Harmonisation (ICH) E9 Guideline entitled Guidance for Industry: Statistical Principles for Clinical Trials¹ and the ICH E3 Guideline entitled Guidance for Industry: Structure and Content of Clinical Study Reports².

4. STUDY OBJECTIVES

4.1 Primary Objective

- To evaluate the relative bioavailability of a single 20 mg dose of LY3337641 as the commercial image tablet (esylate salt) [T1_{fasted}] compared to the Phase 1/2 tablet (diHCl salt) [R_{fasted}].

4.2 Secondary Objectives

- To evaluate the effect of a high-fat meal on the bioavailability of a single 20 mg dose of LY3337641 when administered as the commercial image tablet (esylate salt) [T1_{fed}].
- To evaluate the relative bioavailability of a single 20 mg dose of LY3337641 when administered as the large active pharmaceutical ingredient (API) particle size distribution (PSD) commercial image tablet (esylate salt) [T2_{fasted}] compared to the commercial image tablet (esylate salt) [T1_{fasted}].

- To assess the tolerability of LY3337641 when administered as a single 20 mg dose to healthy subjects.

5. STUDY DESIGN

This is an open-label, 4-period, 4-sequence, randomized, crossover study in healthy subjects. Up to 32 subjects may be enrolled in order to ensure that at least 24 subjects complete the study (ie, complete all 4 treatment periods).

Subjects will receive single oral doses of 20 mg LY3337641 on 4 separate occasions. Each subject will receive the following:

- Reference formulation (R_{fasted}): 20 mg LY3337641 Phase 1/2 tablet (diHCl salt) administered in the fasted state;
- Test formulation 1 ($T1_{\text{fasted}}$): 20 mg LY3337641 commercial image tablet (esylate salt) administered in the fasted state;
- Test formulation 1 ($T1_{\text{fed}}$): 20 mg LY3337641 commercial image tablet (esylate salt) administered in the fed state;
- Test formulation 2 ($T2_{\text{fasted}}$): 20 mg LY3337641 large API PSD commercial image tablet (esylate salt) administered in the fasted state.

Subjects will be randomly allocated to one of the treatment sequences below:

Sequence	Period 1	Period 2	Period 3	Period 4
1	Reference formulation (R_{fasted})	Test formulation 2 ($T2_{\text{fasted}}$)	Test formulation 1 ($T1_{\text{fasted}}$)	Test formulation 1 ($T1_{\text{fed}}$)
2	Test formulation 1 ($T1_{\text{fasted}}$)	Reference formulation (R_{fasted})	Test formulation 1 ($T1_{\text{fed}}$)	Test formulation 2 ($T2_{\text{fasted}}$)
3	Test formulation 1 ($T1_{\text{fed}}$)	Test formulation 1 ($T1_{\text{fasted}}$)	Test formulation 2 ($T2_{\text{fasted}}$)	Reference formulation (R_{fasted})
4	Test formulation 2 ($T2_{\text{fasted}}$)	Test formulation 1 ($T1_{\text{fed}}$)	Reference formulation (R_{fasted})	Test formulation 1 ($T1_{\text{fasted}}$)

In each period, subjects will be admitted to the clinical research unit (CRU) on Day -1. In each treatment period, subjects will be fasted overnight and a single dose of 20 mg LY3337641 will be administered in the morning of Day 1. Subjects will receive a high-fat meal prior to dosing with LY3337641 if applicable. Subjects will reside at the CRU until the collection of the 72-hour PK blood sample.

There will be a washout period of at least 5 days between dose administrations in consecutive periods.

If the investigator decides not to administer the first dose to a subject or not to enroll a subject on a particular day, the subject may be rescheduled to participate in the study; and any procedures performed up to that point may be repeated.

Blood samples will be collected up to 72 hours after each dosing occasion for the measurement of plasma concentrations of LY3337641.

6. TREATMENTS

The following is a list of the study treatment abbreviations that will be used in the TFLs.

Study Treatment Name	Abbreviation	Treatment order in TFLs
20 mg LY3337641 Phase 1/2 tablet (diHCl salt) (Reference fasted)	R _{fasted}	1
20 mg LY3337641 commercial image tablet (esylate salt) (Test 1 fasted)	T1 _{fasted}	2
20 mg LY3337641 commercial image tablet (esylate salt) (Test 1 fed)	T1 _{fed}	3
20 mg LY3337641 large API PSD commercial image tablet (esylate salt) (Test 2 fasted)	T2 _{fasted}	4

7. SAMPLE SIZE JUSTIFICATION

Up to 32 subjects may be enrolled in order to ensure that 24 subjects complete all 4 study periods.

The sample size chosen will provide a precision of 8% for the estimate of the geometric mean ratio in area under the concentration versus time curve (AUC) between the test formulations versus the reference formulation, and between the test formulations administered in the fed versus the fasted state. It means that there is a 90% probability that the half-width of the resulting 90% confidence interval (CI) of the geometric mean ratio in AUC is no larger than 8%. No direct estimate of intra-subject variability is available.

The sample size chosen will provide a precision of 13% for the estimate of the geometric mean ratio in maximum observed drug concentration (C_{max}) between the test formulations versus the reference formulation, and between the test formulations administered in the fed versus the fasted state. It means that there is a 90% probability that the half-width of the resulting 90% CI of the geometric mean ratio in C_{max} is no larger than 13%. No direct estimate of intra-subject variability is available.

Based on Study JPDD, the coefficient of variation (CV%) for AUC and C_{max} were approximately 30% and 50%, respectively, for a 20 mg dose of LY3337641 administered. Assuming that half

of the total CV% is contributed by intra-subject variability, an approximation of the intra-subject variability of 15% for AUC and 25% for C_{max} .

Subjects who are randomized but not complete all 4 treatment periods may be replaced to ensure that enough subjects complete the study. The replacement subject will assume the withdrawn subject's treatment sequence (receiving each treatment allocated).

8. DEFINITION OF ANALYSIS POPULATIONS

The "Safety" population will consist of all subjects who received at least one dose of study drug, whether or not they completed all protocol requirements.

The "Pharmacokinetic" population will consist of all subjects who received at least one dose of study drug and have evaluable PK data. PK data may be excluded from the summary statistics and statical analysis where a subject has an adverse event (AE) of vomiting that occurs at or before 2 times median time of maximum observed drug concentration (t_{max}).

All protocol deviations that occur during the study will be considered for their severity/impact and will be taken into consideration when subjects are assigned to analysis populations.

9. STATISTICAL METHODOLOGY

9.1 General

Data listings will be provided for all data that is databased. Summary statistics and statistical analysis will only be presented for data where detailed in this SAP. For continuous data, summary statistics will include the arithmetic mean, arithmetic standard deviation (SD), median, min, max and N; for log-normal data (e.g. the PK parameters: AUCs and C_{max}) the geometric mean and geometric CV% will also be presented. For categorical data, frequency count and percentages will be presented. Data listings will be provided for all subjects up to the point of withdrawal, with any subjects excluded from the relevant population highlighted. Summary statistics and statistical analyses will generally only be performed for subjects included in the relevant analysis population. For the calculation of summary statistics and statistical analysis, unrounded data will be used.

Mean change from baseline is the mean of all individual subjects' change from baseline values. Each individual change from baseline will be calculated by subtracting the individual subject's baseline value from the value at the timepoint. The individual subject's change from baseline values will be used to calculate the mean change from baseline using a SAS procedure such as Proc Univariate.

Data analysis will be performed using SAS® Version 9.3 or greater.

9.2 Demographics and Subject Disposition

Subject disposition will be listed. The demographic variables age, sex, race, ethnicity, body weight, height and body mass index will be summarized and listed.

9.3 Pharmacokinetic Assessment

9.3.1 Pharmacokinetic Analysis

Noncompartmental methods applied with a validated software program (Phoenix WinNonlin Version 6.4 or later) to the plasma concentrations of LY3337641, will be used to determine the following PK parameters, when possible:

Parameter	Units	Definition
AUC(0-t _{last})	ng•h/mL	area under the concentration versus time curve from time zero to time t, where t is the last time point with a measurable concentration
AUC(0-∞)	ng•h/mL	area under the concentration versus time curve from zero to infinity
%AUC(t _{last} -∞)	%	percentage of AUC(0-∞) extrapolated
C _{max}	ng/mL	maximum observed drug concentration
t _{max}	h	time of maximum observed drug concentration
t _{1/2}	h	half-life associated with the terminal rate constant (λ_z) in non-compartmental analysis
CL/F	L/h	apparent total body clearance of drug calculated after extra-vascular administration
V _z /F	L	apparent volume of distribution during the terminal phase after extra-vascular administration
V _{ss} /F	L	apparent volume of distribution at steady state after extra-vascular administration

Additional PK parameters may be calculated, as appropriate. The software and version used for the final analyses will be specified in the CSR. Any exceptions or special handling of data will be clearly documented within the final study report.

Formatting of tables, figures and abbreviations will follow the Eli Lilly Global PK/PD/TS Tool: NON-COMPARTMENTAL PHARMACOKINETIC STYLE GUIDE. The version of the tool effective at the time of PK analysis will be followed.

General PK Parameter Rules

- Actual sampling times will be used in the final analyses of individual PK parameters, except for non-bolus predose sampling times which will be set to zero. For non-bolus, multiple dose profiles, the predose time will be set to zero unless a time deviation falls outside of the protocol blood collection time window which is considered to impact PK parameter derivation.
- C_{max} and t_{max} will be reported from observed values. If C_{max} occurs at more than one time point, t_{max} will be assigned to the first occurrence of C_{max}.

- AUC parameters will be calculated using a combination of the linear and logarithmic trapezoidal methods (linear-log trapezoidal rule). The linear trapezoidal method will be applied up to t_{max} and then the logarithmic trapezoidal method will be used after t_{max} . The minimum requirement for the calculation of AUC will be the inclusion of at least three consecutive plasma concentrations above the lower limit of quantification (LLOQ), with at least one of these concentrations following C_{max} . AUC(0-∞) values where the percentage of the total area extrapolated is more than 20% will be flagged. Any AUC(0-∞) value excluded from summary statistics will be noted in the footnote of the summary table.
- Half-life ($t_{1/2}$) will be calculated, when appropriate, based on the apparent terminal log-linear portion of the concentration-time curve. The start of the terminal elimination phase for each subject will be defined by visual inspection and generally will be the first point at which there is no systematic deviation from the log-linear decline in plasma concentrations. Half-life will only be calculated when a reliable estimate for this parameter can be obtained comprising of at least 3 data points. If $t_{1/2}$ is estimated over a time window of less than 2 half-lives, the values will be flagged in the data listings. Any $t_{1/2}$ value excluded from summary statistics will be documented in the footnote of the summary table.
- A uniform weighting scheme will be used in the regression analysis of the terminal log-linear portion of the concentration-time curve.
- The parameters based on observed last quantifiable drug concentration (C_{last}) will be reported.

Individual PK Parameter Rules

- Only quantifiable concentrations will be used to calculate PK parameters with the exception of special handling of certain concentrations reported below the lower limit of quantitation (BQL). Concentrations reported as BQL will be set to a value of zero when all of the following conditions are met:
 - The compound is non-endogenous.
 - The samples are from the initial dose period for a subject or from a subsequent dose period following a suitable wash-out period.
 - The time points occur before the first quantifiable concentration.
- All other BQL concentrations that do not meet the above criteria will be set to missing.
- Also, where two or more consecutive concentrations are BQL towards the end of a profile, the profile will be deemed to have terminated and therefore any further quantifiable concentrations will be set to missing for the calculation of the PK parameters unless it is considered to be a true characteristic of the profile of the drug.

Individual Concentration vs. Time Profiles

- Individual concentrations will be plotted utilizing actual sampling times.
- The terminal point selections will be indicated on a semi-logarithmic plot.

Average Concentration vs. Time Profiles

- The average concentration profiles will be graphed using scheduled (nominal) sampling times.
- The average concentration profiles will be graphed using arithmetic average concentrations.
- The predose average concentration for single-dose data from non-endogenous compounds will be set to zero. Otherwise, only quantifiable concentrations will be used to calculate average concentrations.
- Concentrations at a sampling time exceeding the sampling time window specified in the protocol, or $\pm 10\%$, will be excluded from the average concentration profiles.
- Concentrations excluded from the mean calculation will be documented in the final study report.
- A concentration average will be plotted for a given sampling time only if 2/3 of the individual data at the time point have quantifiable measurements that are within the sampling time window specified in the protocol or $\pm 10\%$. An average concentration estimated with less than 2/3 but more than 3 data points may be displayed on the mean concentration plot if determined to be appropriate and will be documented within the final study report.

Treatment of Outliers during Pharmacokinetic Analysis

Application of this procedure to all PK analyses is not a requirement. Rather, this procedure provides justification for exclusion of data when scientifically appropriate. This procedure describes the methodology for identifying an individual value as an outlier for potential exclusion, but does not require that the value be excluded from analysis. The following methodology will not be used to exclude complete profiles from analysis.

Data within an Individual Profile

A value within an individual profile may be excluded from analysis if any of the following criteria are met:

- For PK profiles during single dosing of non-endogenous compounds, the concentration in a predose sample is quantifiable.

- For any questionable datum that does not satisfy the above criteria, the profile will be evaluated and results reported with and without the suspected datum.

Data between Individual Profiles

1. If $n < 6$, then the dataset is too small to conduct a reliable range test. Data will be analyzed with and without the atypical value, and both sets of results will be reported.
2. If $n \geq 6$, then an objective outlier test will be used to compare the atypical value to other values included in that calculation:
 - a. Transform all values in the calculation to the logarithmic domain.
 - b. Find the most extreme value from the arithmetic mean of the log transformed values and exclude that value from the dataset.
 - c. Calculate the lower and upper bounds of the range defined by the arithmetic mean $\pm 3*SD$ of the remaining log-transformed values.
 - d. If the extreme value is within the range of arithmetic mean $\pm 3*SD$, then it is not an outlier and will be retained in the dataset.
 - e. If the extreme value is outside the range of arithmetic mean $\pm 3*SD$, then it is an outlier and will be excluded from analysis.

If the remaining dataset contains another atypical datum suspected to be an outlier and $n \geq 6$ following the exclusion, then repeat step 2 above. This evaluation may be repeated as many times as necessary, excluding only one suspected outlier in each iteration, until all data remaining in the dataset fall within the range of arithmetic mean $\pm 3*SD$ of the log-transformed values.

Reporting of Excluded Values

Individual values excluded as outliers will be documented in the final report. Approval of the final report will connote approval of the exclusion. Insert from PKAP (note PKAP should detail WinNonlin version)

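### SAP 9.3.1 conflicts on whether a flagged outlier is excluded, and at this study's size it requires no all-data ratio and CI beside the reduced result

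*SAP*

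**What the plan says.** The part of SAP 9.3.1 on treatment of outliers begins with discretion: "Application of this procedure to all PK analyses is not a requirement". It describes the procedure as support for leaving data out where that is scientifically justified, without defining the term. It adds that identifying an outlier "does not require that the value be excluded from analysis". It also sets a limit: "The following methodology will not be used to exclude complete profiles from analysis".

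Three rules follow.

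- **Within a profile**, for a questionable datum not covered by the listed criterion: "the profile will be evaluated and results reported with and without the suspected datum".
- **Between profiles, n<6**: "Data will be analyzed with and without the atypical value, and both sets of results will be reported".
- **Between profiles, n≥6**: take the most extreme log value and compare it with the mean ± 3 SD of the others. If it lies outside, "then it is an outlier and will be excluded from analysis". On repetition: "This evaluation may be repeated as many times as necessary, excluding only one suspected outlier in each iteration".

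On reporting: "Individual values excluded as outliers will be documented in the final report". SAP 9.3.2 then fits one mixed model to log AUC(0-∞), AUC(0-tlast) and Cmax for all three comparisons. It plans no sensitivity analysis.

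**The concern.** The opening says that an identified outlier need not be excluded; step 2e says that it will be. Two analysts could follow the same text and report different ratios. The choice would be made after the data are seen, in an open-label study.

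The safeguard of showing both results is present for small sets and single profiles but absent from the branch that governs here. In a relative bioavailability study, an isolated low exposure on one tablet may be a real formulation signal. Protocol 3.1 says that neither salt is considered highly soluble and that the effect of particle size in vivo needs to be understood. If such values are removed from the model, the ratio moves toward 1 and the interval narrows. This could affect T1/R (primary) as well as T2/T1.

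**Working it through.** **1. Which branch applies.** SAP 7 plans 24 completers, so each treatment has about 24 values. At the interim (24 subjects through Period 3), each treatment appears in 3 of the 4 sequences by Period 3, giving 18 values. T1 fasted and R fasted both appear in 2 of the 4, giving the SAP's 12 subjects. All of these are ≥6, so no with/without result is required at either analysis.

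**2. The plan's own precision, as a baseline.** SAP 7 assumes intra-subject CVs of 15% (AUC) and 25% (Cmax). Log half-width = t(0.95, df) × σw × √(χ²(0.90, df)/df) × √(2/n), with σw = √ln(1+CV²). For n=24 and df=23:

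- AUC: σw = √ln(1.0225) = 0.149; half-width 0.0871; 1 − e^(−0.0871) = 8.3%
- Cmax: σw = √ln(1.0625) = 0.246; half-width 0.1437; 1 − e^(−0.1437) = 13.4%

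These agree with the stated 8% and 13%, which are not in dispute.

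**3. Clean data.** Under normal log values, the leave-one-out statistic divided by √(1+1/(n−1)) follows t on n−2 df. For n=24 the cut-off is 3/√(1+1/23) = 2.94 on 22 df, and n × p = 0.183 as an upper bound. Simulation gives 0.181. So about 18% of 24-value sets would lose a value if every set were tested; the SAP tests only a value judged atypical, so real use may be rarer. The effect is negligible. Coverage of the 90% CI, all data against rule, is 0.903 against 0.896 (AUC) and 0.892 against 0.886 (Cmax), and the median shift in the ratio is 0.

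**4. Which losses the rule catches.** SAP 7 gives total CVs of 30% and 50%, so the total log SDs are √ln(1.09) = 0.294 (AUC) and √ln(1.25) = 0.472 (Cmax).

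- An 80% cut is ln(0.2) = −1.609, which is 5.5 SD for AUC and 3.4 SD for Cmax.
- A 50% cut is ln(0.5) = −0.693, which is 2.4 SD and 1.5 SD.

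Deep AUC losses are therefore nearly always flagged and 50% losses mostly are not.

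**5. Assumed low exposures.** The documents give no failure rate or depth, so these cases are assumptions shown as a range. The setup is 24 subjects, the four protocol sequences, step 2 run per treatment and repeated, a fixed-subject version of the 9.3.2 model, and 4,000 trials per case. The true mean log ratio is (k/24) × ln(1−cut); for 2 of 24 cut by 80%, (2/24) × (−1.609) = −0.134, a ratio of 0.874. The table is for T2/T1 with exactly k failures, dropping every flagged value.

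| Case | Ratio, all data → rule | Coverage, all data vs rule |
|---|---|---|
| AUC, 2 cut 80% | 0.876 → 0.999 | 1.00 vs 0.11 |
| AUC, 1 cut 70% | 0.951 → 0.992 | 0.97 vs 0.73 |
| AUC, 4 cut 70% | 0.818 → 0.850 | 1.00 vs 0.84 |
| AUC, 2 cut 50% | 0.944 → 0.957 | 0.95 vs 0.88 |
| Cmax, 2 cut 80% | 0.875 → 0.944 | 0.97 vs 0.69 |
| Cmax, 2 cut 50% | 0.944 → 0.948 | 0.93 vs 0.91 |

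In the first row the log half-width falls from 0.131 to 0.075. Typical intervals are therefore 0.876 × e^(±0.131) = 0.77 to 1.00 and 0.999 × e^(±0.075) = 0.93 to 1.08. T1/R behaves the same way (0.874 → 0.997). All-data coverage exceeds 0.90 because fixing k makes the sample failure fraction equal the truth. If each subject instead fails with probability 2/24, the first row becomes 0.875 → 0.957, with coverage 0.77 against 0.18.

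**6. The bar on complete profiles.** Suppose AUC and Cmax of the same 2 profiles are both cut by 80%. The rule flags both in 54% of failed profiles, AUC only in 44% and neither in 2%. Now suppose the bar means that AUC is kept whenever both are flagged, with an assumed AUC–Cmax log correlation of 0.7. The ratio then moves from 0.876 to 0.930, the half-width from 0.131 to 0.108, and coverage under the rule is 0.68. With random failures the figures are 0.878 to 0.918 and coverage 0.56.

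**The case against.** The strongest reply is that the opening governs: running the test is optional and tied to scientific justification, and step 2e only states the outcome once it is run. That softens the conflict but does not remove it. The opening says that even an identified outlier need not be excluded, and the justification is undefined.

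Scope is a fair objection. The rule sits under pharmacokinetic analysis, and the nearby AUC(0-∞) footnote rule speaks only of summary statistics. SAP 8, by contrast, names both summary statistics and statistical analysis for its vomiting exclusion. A reader might infer that step 2e certainly alters the 9.3.2 ratios. The SAP does not say so, and the PKAP or the TFL shells, which are not available here, may settle it. Equally, the exclusion wording is not confined to summary statistics.

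A reader might also infer concealment. The documents do not support that: excluded values are documented, an AUC(0-∞) left out of summary statistics is footnoted, special handling must be described and data are listed. The all-data ratio could be recomputed from the listings; the gap is that the report need not show it.

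Finally, the harm depends on assumed failures counted as real product behaviour. If a low value is a sampling or assay artefact, excluding it helps. No equivalence margin is stated, so no pass/fail decision is at stake. These points stand and limit the size of the concern.

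**Conclusion.** The concern holds as a wording conflict and a reporting gap. SAP 9.3.1 does not settle whether an identified outlier is excluded. For n≥6 it permits removal on a between-subject test without a documented cause and without an all-data ratio and 90% CI.

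Any effect on the endpoints is conditional on exclusions reaching 9.3.2. It is then negligible in clean data, small for 50% losses, and material only for deep, isolated low exposures. For AUC with 2 of 24 cut by 80%, the ratio goes from about 0.88 to 1.00 if all flagged values are dropped, or to about 0.93 on the broad reading of the profile bar. The inference that the rule distorts ordinary results is not supported. Importance is minor to worth fixing; confidence is moderate, because scope and failure pattern are both unstated.

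**What to change.** (a) State in SAP 9.3.2 that the primary analysis of AUC and Cmax uses all evaluable values, except those with a documented dosing, sampling or bioanalytical cause and those excluded under the vomiting rule in SAP 8.

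(b) Change step 2e so that a value outside the range is flagged as an outlier. Edit the iteration paragraph to match, so that values are set aside for testing only.

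(c) Whenever a value is flagged, also report the 9.3.2 ratio and 90% CI without it, labelled as a sensitivity analysis. This leaves one named primary result.

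The cost is a few sentences and one extra model run when something is flagged. The primary CI will be wider when a true extreme value is present.
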